## 6.2.2 Early Clinical Response in the microITT Analysis Set

The secondary efficacy analysis of ECR will be conducted in the microITT Analysis Set. An additional analysis will be conducted in microITT-2 and emicroITT Analysis Sets (see Section 6.3). For the microITT and microITT-2 Analysis Sets, the percentage of subjects considered responders for ECR is defined using the following formula (where the denominator is comprised of the total number of subjects in the microITT and microITT-2 Analysis Sets):

$$\frac{\text{Number of subjects who are a responder}}{(\text{Number of subjects who are a responder} + \text{Number of subjects who are a non-responder} + \text{Number of indeterminate subjects})} \times 100\%$$

## 6.2.3 By-Pathogen Microbiological Response

By-pathogen microbiological responses are eradication, presumed eradication, persistence, presumed persistence and indeterminate, as defined in Table 5. Microbiological responses of eradication and persistence are based on comparing the baseline pathogen(s) to post-baseline pathogens, where post-baseline organisms are identified from post-baseline cultures and considered pathogens based on the criteria in Section 4.0. If a pathogen is persistent at the EOT Visit, the persistence is carried forward to the TOC and LFU Visits. If a pathogen is presumed persistent at the EOT Visit, the presumed persistence is carried forward to the TOC and LFU Visits, unless a repeat culture is obtained between the EOT and TOC or EOT and LFU Visits, respectively, which shows persistence. Baseline pathogens identified by a modality other than culture of a blood or respiratory sample (ie, pathogen from serology, urine antigen or PCR) can only have a presumed or indeterminate microbiological response.

**Table 5. By-Pathogen Microbiological Response at EOT, TOC and LFU**

Outcome		EOT	TOC and LFU
Success	Eradication	The baseline causative pathogen was absent from repeat culture(s) obtained at EOT (ie, the post-baseline culture showed no growth or the post-baseline culture did not grow the same pathogen as isolated at baseline, or the same organism(s) was present but did not meet the definition of pathogen as defined in Section 4.0).	The baseline causative pathogen was absent from repeat culture(s) obtained between EOT and TOC or EOT and LFU, respectively (ie, the post-baseline culture showed no growth or the post-baseline culture did not grow the same pathogen as isolated at baseline, or the same organism(s) was present but did not meet the definition of pathogen as defined in Section 4.0).
	Presumed eradication	The IACR was success and culture was not repeated at EOT.	The IACR was success (TOC) or sustained success (LFU) and culture was not repeated (at TOC and LFU, respectively).
Failure	Persistence	The baseline causative pathogen was isolated in repeat culture(s) obtained at EOT.	Persistence at EOT is carried forward or a culture obtained after EOT and up to and including TOC grew the same pathogen identified at baseline (TOC). Persistence at TOC is carried forward or a culture obtained after TOC and up to an including LFU grew the same pathogen identified at baseline (LFU).

	Presumed persistence	The IACR was failure and culture was not repeated at EOT.	The IACR was failure (TOC) or prior failure/relapse (LFU) and culture was not repeated (at TOC and LFU, respectively) and no cultures demonstrated persistence (between EOT and TOC and EOT and LFU, respectively).
Indeterminate		The IACR was indeterminate and culture was not repeated at EOT.	The IACR was indeterminate and culture was not repeated (at TOC and LFU, respectively) and no cultures demonstrated persistence (between EOT and TOC and EOT and LFU, respectively).

The by-pathogen microbiological response success rate at the EOT, TOC and LFU Visits in the microITT and microITT-2 (TOC Visit only; see Section 6.3) Analysis Sets is calculated as follows:

$$\frac{\text{Number of subjects who are a success for the specific pathogen}}{\text{(Number of subjects who are a success for the specific pathogen + Number of subjects who are a failure for the specific pathogen + Number of subjects who are indeterminate for the specific pathogen)}}$$

Subjects with an indeterminate microbiological response at the EOT, TOC and LFU Visits will be excluded from the ME Analysis Sets. Thus, the by-pathogen microbiological response success rate is calculated as follows:

$$\frac{\text{Number of subjects who are a success for the specific pathogen}}{\text{(Number of subjects who are a success for the specific pathogen + Number of subjects who are a failure for the specific pathogen)}}$$

Subjects who have the same pathogen isolated at baseline from more than 1 specimen type are counted only once in the determination of by-pathogen microbiological response. If a subject has the same baseline pathogen identified by culture of blood or respiratory sample and another modality and a repeat culture is obtained, microbiological response is based on the post-baseline culture results. If a subject has the same baseline pathogen identified from culture of blood and a respiratory sample, eradication requires the baseline pathogen to be absent from respiratory sample culture without evidence of ongoing bacteremia. Persistence requires the baseline pathogen to be present from either the blood or respiratory sample culture.

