#### Success includes:

- Eradication: the baseline causative pathogen was absent from repeat culture(s).
- Presumed eradication: the IACR was Success, and culture was not repeated.

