#### • Failure includes:

- Persistence: the baseline causative pathogen was isolated in repeat culture(s).
- Presumed persistence: the IACR was Failure and a culture was not repeated.

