## 6.2 Secondary Efficacy Outcomes

Secondary efficacy outcomes include:

- Percentage of subjects with IACR of success at the TOC Visit in the mITT and CE-TOC Analysis Sets
- Percentage of subjects with ECR of responder in the microITT Analysis Set
- Percentage of subjects with IACR of success at the TOC Visit in the microITT and ME-TOC Analysis Sets
- Proportion of subjects with a by-pathogen microbiologic response of success at the TOC Visit in the microITT and ME-TOC Analysis Sets
- All-cause mortality (ACM) through Day 28 in the ITT Analysis Set

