### **8.5.3.4 By-Pathogen Microbiological Response at the TOC Visit in the microITT and ME-TOC Analysis Sets**

The proportion of subjects with a microbiological response of success by baseline pathogen (and where relevant, the susceptibility phenotype) at the TOC Visit will be tabulated separately by treatment group for subjects in the microITT and ME-TOC Analysis Sets. Distinct pathogens are based on genus and species and where relevant, the susceptibility phenotype as defined in [Table 8](#).

For all by-pathogen analyses, subjects with a pathogen of the same genus and species with more than 1 phenotype, for example both MRSA and MSSA, will be counted once for each phenotype and once for the overall tabulation of the pathogen, for example, *Staphylococcus aureus*.

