#### **8.5.4.2 Microbiological Response Measures**

The number and percentage of subjects determined to have a by-subject microbiological response of success (eradication or presumed eradication), failure (persistence or presumed persistence) or indeterminate at the EOT, TOC and LFU Visits will be tabulated by treatment group for subjects in the microITT, microITT-2 (TOC Visit only) and ME-EOT (EOT Visit), ME-TOC (TOC Visit) and ME-LFU (LFU Visit) Analysis Sets. A 2-sided unadjusted 95% CI

for the difference in by-subject microbiological response success rates between the lefamulin and moxifloxacin treatment groups will be provided.

The proportion of subjects with a microbiological response of success by baseline pathogen (and where relevant, the susceptibility phenotype) at the TOC Visit will be tabulated separately by treatment group for subjects in the microITT-2 Analysis Set. The proportion of subjects with a microbiological response of success by baseline pathogen (and where relevant, the susceptibility phenotype) at the EOT Visit will be tabulated separately by treatment group for subjects in the microITT and ME-EOT Analysis Sets. The proportion of subjects with a microbiological response of sustained success by baseline pathogen (and where relevant, the susceptibility phenotype) at the LFU Visit will be tabulated separately by treatment group for subjects in the microITT and ME-LFU Analysis Sets.

A by-subject listing will present the by-pathogen and by-subject microbiological response at the EOT, TOC and LFU Visits in the ITT Analysis Set. A second by-subject listing will present the by-pathogen and by-subject microbiological response at the EOT, TOC and LFU Visits for non-responders, clinical failures, or subjects with persistence.

The proportion of subjects with a microbiological response of success at the TOC Visit by baseline pathogen (and where relevant, the susceptibility phenotype) and MIC to study drug received and by baseline pathogen (and where relevant, the susceptibility phenotype) and disk diffusion zone diameter will be determined for each pathogen isolated at baseline in the microITT and ME-TOC Analysis Sets.

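### SAP Table 5 scores regrowth of the baseline organism from a below-cut-off repeat sputum as Eradication, contrary to the protocol; the effect is clearest at EOT and narrower at TOC

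*SAP*

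**What the plan says.** **Protocol.** Section 9.4.2.2, like the synopsis, uses two plain definitions. Under Success it has "Eradication: the baseline causative pathogen was absent from repeat culture(s". Under Failure it has "Persistence: the baseline causative pathogen was isolated in repeat culture(s". Neither carries a Gram-stain condition.

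**SAP Table 5.** In both the EOT column and the TOC/LFU column, Eradication also covers the case "or the same organism(s) was present but did not meet the definition of pathogen as defined in Section 4.0". Section 6.2.3 applies the Section 4.0 criteria to organisms grown after baseline, and Section 4.0 limits post-baseline pathogens to those found by culture. For *S. pneumoniae*, *H. influenzae*, *S. aureus*, *M. catarrhalis* and *M. pneumoniae*, Sections 4.1 and 4.2 accept a sputum culture when the Gram stain shows more than 25 PMNs and fewer than 10 SECs per low-power field. *L. pneumophila* in sputum counts whatever the Gram stain.

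**TOC rules.** The Eradication row reads "The baseline causative pathogen was absent from repeat culture(s) obtained between EOT and TOC or EOT and LFU, respectively". The Persistence row carries EOT persistence forward, or uses "a culture obtained after EOT and up to and including TOC grew the same pathogen identified at baseline (TOC". Section 6.2.3 carries presumed persistence at EOT forward unless a later culture shows persistence. Section 7.6 carries an EOT IACR of Failure, and an EOT by-subject microbiological failure, to TOC.

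**Use.** Section 6.2 lists as a secondary outcome "Proportion of subjects with a by-pathogen microbiologic response of success at the TOC Visit in the microITT and ME-TOC Analysis Sets". Section 8.5.3.4 says that this success proportion "at the TOC Visit will be tabulated separately by treatment group for subjects in the microITT and ME-TOC Analysis Sets", with no interval. For by-subject response, Section 8.5.4.2 says that a 95% CI "for the difference in by-subject microbiological response success rates between the lefamulin and moxifloxacin treatment groups will be provided".

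**The concern.** The clause records the presence of the organism as its eradication. A quality cut-off is a fair reason not to call growth from a poor sputum persistence, because such growth may be oral contamination or colonization. That makes the specimen uninformative. It does not show that the pathogen has gone.

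The rule also reverses the order of the evidence. At EOT, a clinical failure with no repeat culture is Presumed persistence, a Failure. The same clinical failure whose poor sputum regrows the organism is Eradication, a Success. Protocol Section 6.15.1 makes clinical failures a likely source of repeat sputum: it is repeated only when clinically indicated, and, if possible, at discontinuation for clinical failure.

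At stake are the by-pathogen success rates and the by-subject rates built from them (SAP Table 6). The clause can only raise these rates, and a reader of Section 9.0 would not learn that the definition had changed.

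**Working it through.** No stated sample size, power or alpha depends on this definition, so there is no figure in the plan to reproduce. The check applies the rules case by case.

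**1. Which Gram stains trigger the clause.** SAP Section 4.1 ranks nine PMN/SEC categories. Only the first meets the cut-off, so regrowth in 9 − 1 = 8 of 9 categories falls under the clause for each of the five organisms. For *L. pneumophila* it is 0 of 9. Under the protocol, regrowth is Eradication in 0 of 9 for all. These are categories, not frequencies.

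**2. EOT column.** Four culture results by three IACR values give 4 × 3 = 12 rule cells. S, F and I are microbiological Success, Failure and Indeterminate, in the order IACR Success / Failure / Indeterminate.

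| Repeat culture at EOT | SAP | Protocol | Proposed fix |
|---|---|---|---|
| None | S F I | S F I | S F I |
| No growth | S S S | S S S | S S S |
| Regrowth, meets cut-off | F F F | F F F | F F F |
| Regrowth, below cut-off | S S S | F F F | S F I |
| Success cells | 1+3+0+3 = 7 | 1+3+0+0 = 4 | 1+3+0+1 = 5 |

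The SAP differs from the protocol in 3 cells, all in the last culture row. The fix changes 2 of these (IACR Failure and Indeterminate). It still differs from the protocol in 2 (IACR Success and Indeterminate). The Indeterminate cell cannot arise in the ME sets, which exclude an indeterminate IACR.

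**3. TOC.**
- *Adequate regrowth at EOT.* Persistence is carried forward, and a later poor sputum cannot overturn it.
- *IACR Failure at EOT, no EOT culture.* Presumed persistence is carried forward under Section 6.2.3, and Section 7.6 carries the by-subject failure. The TOC Eradication row would nevertheless give Success if a later culture showed no growth or below-cut-off regrowth. The SAP does not say which rule governs.
- *IACR Failure at EOT, below-cut-off regrowth at EOT, no later culture.* The result is Success at EOT. The IACR of Failure carries to TOC. If the TOC window means cultures after EOT, the result there is Presumed persistence, a Failure. If the window includes the EOT culture, the Eradication row is also met and the Success reaches TOC.
- *Below-cut-off regrowth after EOT, IACR Failure or Indeterminate at TOC.* The Eradication row gives Success. With no such culture the result would be Presumed persistence or Indeterminate. This is the main group affected at TOC.
- *Below-cut-off regrowth after EOT, IACR Success at TOC.* The result is Success under the SAP and under the fix, and Failure under the protocol.

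No TOC or LFU cell count is given, because it depends on how the window is read.

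**4. Size per subject.** One reclassified subject moves a pathogen's success rate by 100/n points. For assumed n of 10, 20 and 40: 100/10 = 10.0, 100/20 = 5.0, 100/40 = 2.5.

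**The case against.** **One pathogen definition before and after baseline is coherent.** Protocol Section 6.15.1 itself uses the same figures for an adequate sputum, the protocol definitions refer to the causative pathogen, and Section 9 leaves analytic detail to the SAP. This supports keeping the cut-off. It does not support scoring what falls below it as absence. Protocol Section 9.8 already bases a missing microbiological response on the IACR, which is the natural treatment of an uninformative specimen. SAP Section 6.2.3 itself requires absence from the respiratory culture when the pathogen was found in both blood and a respiratory sample.

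**The criteria may be sufficient rather than exclusive.** Sections 4.1 and 4.2 say when an organism is always a pathogen, Section 4.0 has pathogens determined for each subject, and the detail sits in the Evaluability Review Plan, which is not among the documents. Blinded review could therefore shrink the affected group. It cannot empty the clause, which presupposes organisms that are present but not pathogens. Section 5.8 also treats the cut-off as defining a sputum pathogen, although it speaks of baseline.

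**TOC is largely protected.** This stands. A reader might infer that clinical failures at EOT become successes in the TOC secondary outcome. On the ordinary reading they do not, because the EOT failure is carried forward. A reader might also see the different windows in the two TOC rows as a second substantive error. It is mostly wording, since EOT persistence is carried forward separately.

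**The fix is not the protocol's rule either.** Also true. It departs from the protocol in 2 cells and leaves no growth from a poor sputum as Eradication, even in a clinical failure. The latter follows the protocol's own definition. The former is why a Section 9.0 entry and a sensitivity table are needed.

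**Conclusion.** The Eradication definition in SAP Table 5 is wrong as written, in both columns, and the departure from protocol Section 9.4.2.2 is undisclosed. The effect is plain at EOT. At TOC it is narrower: mainly subjects with below-cut-off regrowth after EOT and an IACR of Failure or Indeterminate. It is wider only if the TOC window includes the EOT culture.

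The scope is sputum cultures of culture-identified baseline pathogens other than *L. pneumophila*. BAL, pleural fluid and blood cultures carry no Gram-stain condition. Pathogens found only by serology, urinary antigen or PCR can have only a presumed or indeterminate response.

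The size is unknown, because the documents give no counts of repeat sputa or of their quality. The 7, 4 and 5 of 12 are rule cells, not subjects, and the 100/n shifts rest on assumed denominators.

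A reader might infer that the clause favours lefamulin or threatens the main conclusions. The documents do not support that. The rule is the same in both arms, the by-pathogen table has no interval or test, and ECR, IACR and the non-inferiority conclusions do not use it. The correction should be made because it is cheap and the affected rates are reported by pathogen, where a small denominator would let one subject matter.

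**What to change.** 1. Delete the clause on organisms present but not meeting the pathogen definition from Eradication in both columns of Table 5.
2. State that a below-cut-off sputum that regrows the baseline organism is treated as culture not repeated, so that the IACR-based presumed or indeterminate response applies. No growth stays Eradication.
3. Align the rest of Section 6.2.3 (the sentence on post-baseline organisms, and the closing rules for pathogens found by more than one specimen or modality) and the microbiological rules in Section 7.6.
4. State whether the TOC window includes the EOT culture, and whether the carry-forward of EOT presumed persistence or the TOC Eradication row takes precedence.
5. List the remaining departure from protocol Section 9.4.2.2 in SAP Section 9.0.
6. Add one sensitivity table that scores any regrowth of the baseline pathogen as Persistence, as the protocol defines it.

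The cost is SAP wording and one table. Reported microbiological success rates may be slightly lower.

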#### **6.2.4 28-Day All-Cause Mortality**

The outcome measure of all-cause mortality (ACM) is defined as deceased on or before Study Day 28.

Subjects with an LFU visit on Study Day 27 will be considered alive on Study Day 28 unless known to have died on Study Day 28. Other subjects who are not known to be alive or deceased as of Study Day 28 will be defined as deceased and included in the numerator and denominator for the calculation of the ACM rate. The 28-day ACM rate is defined by the following formula:

$$\frac{\text{Number of subjects deceased}}{\text{(Number of subjects alive at Day 28 + Number of subjects deceased)}} \times 100\%$$

### 6.3 Additional Efficacy Outcomes

Additional efficacy outcomes specified in the protocol include:

- Proportion of subjects with an ECR of responder by baseline pathogen in the microITT Analysis Set
- Percentage of subjects with an IACR of success at the EOT Visit in the mITT and CE-EOT Analysis Sets, and at the LFU Visit (sustained success) in the mITT and CE-LFU Analysis Sets
- Proportion of subjects with an IACR of success by baseline pathogen at the TOC Visit in the microITT and ME-TOC Analysis Sets, and at the LFU Visit (sustained success) in the microITT and ME-LFU Analysis Sets
- Number and percentage of subjects with a by-subject microbiologic response of success at the TOC Visit in the microITT and ME-TOC Analysis Sets
- Proportion of subjects with an ECR of responder PLUS improvement in vital signs in the ITT Analysis Set

Other additional efficacy outcomes specified in this SAP include:

- Percentage of subjects with an ECR of responder in the microITT-2 and emicroITT Analysis Sets
- Proportion of subjects with an ECR of responder by baseline pathogen in the microITT-2 Analysis Set
- Proportion of subjects with an ECR of responder by baseline pathogen and MIC to study drug received in the microITT Analysis Set
- Proportion of subjects with an ECR of responder by baseline pathogen and disk diffusion zone diameter to study drug received in the microITT Analysis Set
- Proportion of subjects with an ECR of responder by baseline pathogens identified from blood specimens in the microITT Analysis Set
- Percentage of subjects with an IACR of success at the TOC Visit in the microITT-2 and emicroITT Analysis Sets, at the EOT Visit in the microITT and ME-EOT Analysis Sets, and at the LFU Visit (sustained success) in the microITT and ME-LFU Analysis Sets
- Proportion of subjects with an IACR of success by baseline pathogen at the TOC Visit in the microITT-2 Analysis Set, and at the EOT Visit in the microITT and ME-EOT Analysis Sets
- Proportion of subjects with an IACR of success at the TOC Visit by baseline pathogen and MIC to study drug received in the microITT and ME-TOC Analysis Sets
- Proportion of subjects with an IACR of success at the TOC Visit by baseline pathogen and disk diffusion zone diameter to study drug received in the microITT and ME-TOC Analysis Sets

- Proportion of subjects with an IACR of success at the TOC Visit by baseline pathogens identified from blood specimens in the microITT Analysis Set
- Proportion of subjects with a by-pathogen microbiologic response of success at the TOC Visit in the microITT-2 Analysis Set, at the EOT Visit in the microITT and ME-EOT Analysis Sets, and at the LFU Visit in the microITT and ME-LFU Analysis Sets
- Proportion of subjects with a microbiologic response of success at the TOC Visit by baseline pathogen and MIC to study drug received in the microITT and ME-TOC Analysis Sets
- Proportion of subjects with a microbiologic response of success at the TOC Visit by baseline pathogen and disk diffusion zone diameter to study drug received in the microITT and ME-TOC Analysis Sets
- Number and percentage of subjects with a by-subject microbiologic response of success at the TOC Visit in the microITT-2 Analysis Set, at the EOT Visit in the microITT and ME-EOT Analysis Sets, and at the LFU Visit in the microITT and ME-LFU Analysis Sets

### 6.3.1 By-Subject Microbiological Response at the EOT, TOC and LFU Visits

By-subject microbiological response is determined from the by-pathogen microbiological responses as defined in

Table 6.

**Table 6. By-Subject Microbiological Response at EOT, TOC and LFU**

Outcome		Definition
Success	Eradication or Presumed eradication	All baseline pathogens have a by-pathogen microbiological response of eradication or presumed eradication at the specified visit.
Failure	Persistence or Presumed persistence	At least 1 baseline pathogen has a by-pathogen microbiological response of persistence or presumed persistence at the specified visit.
Indeterminate		At least 1 baseline pathogen has a by-pathogen microbiological response of indeterminate and none have a by-pathogen microbiological response of persistence or presumed persistence.

The by-subject microbiological response success rate at the EOT, TOC and LFU Visits in the microITT and microITT-2 (TOC Visit only) Analysis Sets is calculated as follows:

$$\frac{\text{Number of subjects who are a success}}{(\text{Number of subjects who are a success} + \text{Number of subjects who are a failure} + \text{Number of subjects who are indeterminate})} \times 100\%$$

Subjects with an indeterminate microbiological response at the EOT, TOC and LFU Visits will be excluded from the ME Analysis Sets. Thus, the by–subject microbiological response success rate is calculated as follows:

$$\frac{\text{Number of subjects who are a success}}{(\text{Number of subjects who are a success} + \text{Number of subjects who are a failure})} \times 100\%$$

